  In one of the dose escalation cohorts, administration of a single dose of BAY 1163877 using the tablet formulation on Cycle 1, Day -3 followed by solution formulation starting Cycle 1 Day 1 as described above.
- Study Part 2 / MTD expansion (sqNSCLC + LAC + BC + SCCHN): Individual number of 21-day Cycles with continuous BAY 1163877 monotherapy (tablet or solution) until disease progression or as long as clinical benefit is assumed by the investigator or until unacceptable toxicity occurs.
- Study Part 1 (MTD expansion cohort) and Study Part 2 (sqNSCLC + LAC + BC + SCCHN) / "Food Effect Assessment":
   Approximately 8 subjects will receive single doses of BAY 1163877 on Cycle 1, Day -3 (after consumption of a high-fat, high-calorie breakfast) and on Cycle 1, Day 1 (after an overnight fast of at least 8 hours) followed by treatment according to the schedule described above starting on Cycle 1, Day 3.
- Study Part 3 / MTD expansion "Safety cohort" (sqNSCLC + LAC + BC): Individual number of 21-day Cycles with continuous BAY 1163877 monotherapy (tablet) until disease progression or as long as clinical benefit is assumed by the investigator or until unacceptable toxicity occurs. 

Note: Treatment with BAY 1163877 at MTD in Part 1 (expansion cohort "all comer"), Part 2 (expansion cohort sqNSCLC + LAC + BC + SCCHN), and Part 3 (expansion cohort "Safety cohort", sqNSCLC + LAC + BC) can run in parallel.

- Follow-up (FU)
  - End of Treatment (EOT) visit 0-14 days after last dose of BAY 1163877
  - Follow-up (FU) visit at 30-35 days after dose of BAY 1163877

The first screening visit is scheduled within 7 days / within 28 days before administration of the first dose of BAY 1163877. The informed consent form will be signed by the subject before or at the first screening visit (please refer to Section 13.2). The screening period ends just before start of treatment.

The treatment period starts on the day of the first administration of study treatment either on Cycle 1, Day 1 or on Cycle 1, Day -3 ("tablet bridging cohort" and "food effect assessment") and ends with the last day when the study medication is administered in Cycle X. The length of treatment period may vary from subject to subject dependent on the number of individual treatment cycles. A Cycle for this study is defined as 21 days. There will be no break between cycles.

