Approximately 8 subjects enrolled in the MTD expansion cohorts (study Part 1 and Part 2) will receive single doses of BAY 1163877 on Cycle 1, Day -3, after consumption of a high-fat, high-calorie breakfast and on Cycle 1, Day 1, after an overnight fast of at least 8 hours followed by treatment according to the schedule described above starting on Cycle 1, Day 3.

Subjects without PK assessment in study Part 2 will receive BAY 1163877 (tablet or solution) twice daily from Cycle 1, Day 1 ongoing.

At home, subjects will document the intake of study drug in a diary (see Section 8.7).

[figure not shown]
Subjects will continue receiving treatment until tumor progression, unacceptable toxicity, consent withdrawal, or subject withdrawal from the study at the discretion of the Investigator or his/her designated associate(s), see Section 7.2.1. As long as, in the judgment of the subject and the investigator, some benefit with evidence of tumor reduction or stable disease is being derived, dosing with BAY 1163877 may continue.

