## 8.3 Treatment assignment

After completion of the screening examinations, subjects who meet the entry criteria will be placed in the current cohort at the specified dose level. A random list is not necessary because this is a non-randomized open label clinical trial. All subjects will be assigned a unique screening number (SNR), whether or not they are treated after the first signed informed consent. For subject identification, see Section 7.3.

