## 8.4.2.1 Dosing schedule - amended

BAY 1163877 will be given in cycles. Each cycle lasts 21 days. There will be no break between treatment cycles.

Subjects will receive either the solution (IMP 1) or the tablet (IMP 2) formulation of BAY 1163877, except for subjects in the "tablet bridging cohort" who will receive both a single dose using the tablet formulation and multiple doses using the solution formulation.

Study Part 1 / dose escalation + MTD expansion cohort (all comer):

Cycle 1 Day -3 ("tablet bridging cohort" only): Single-dose administration of

BAY 1163877 tablet formulation on Cycle 1, Day -3; thereafter continuation with solution formulation starting on Cycle 1, Day 1 (see dosing schedule

below)

Cycle 1: Single-dose administration of BAY 1163877 on

Cycle 1, Day 1 (in the morning)

No administration of BAY 1163877 on Cycle 1,

Day 2 ("drug-free day")

Twice daily administration of BAY 1163877 on

Days 3-21

Cycle 2 and subsequent cycles: Twice daily administration of BAY 1163877 on

Days 1-21.

Study Part 2 / dose expansion (sqNSCLC + LAC + BC + SCCHN):

- Subjects participating in PK assessments will follow the dosing regimen specified for study Part 1.
- Subjects without PK assessment will receive BAY 1163877 twice daily from Cycle 1, Day 1 ongoing.

Study Part 1 (MTD expansion cohort) or Study Part 2 / "Food Effect Assessment": Approximately 8 subjects will receive single doses of BAY 1163877 on Cycle 1, Day -3 (after consumption of a high-fat, high-calorie breakfast) and on Cycle 1, Day 1 (after an overnight fast of at least 8 hours). BAY 1163877 will not be administered on Cycle 1, Day -2 and Day -1, in the evening of Cycle 1, Day 1 and on Cycle 1, Day 2.

[figure not shown]
Study Part 3 / MTD expansion "Safety cohort" (sqNSCLC + LAC + BC):

• Subjects will receive BAY 1163877 twice daily from Cycle 1, Day 1 ongoing.

-

<sup>48 Part 3 added by Amendment 7, see section 15.6.2.14

<sup>49 Part 3 - Safety cohort - was added by Amendment 7, see section 15.6.2.15

17 Oct 2018 Version 8.0 Page: 60 of 395

Evidence of tumor progression, unacceptable toxicity, consent withdrawal or subject's withdrawal from the study at the discretion of the Investigator may lead to termination of treatment (see Section 7.2.1).

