## 8.9.1 Drug-drug interactions relevant for BAY 1163877

Oxidative metabolism of BAY 1163877 is mainly catalyzed by CYP3A4 and CYP1A1 and to a lesser extent by CYP2C9. Therefore, drugs and herbal preparations that are strong inhibitors and inducers of CYP3A4 are not permitted during the study. Currently, there are no known approved drugs or herbal preparations that are strong CYP1A1 inhibitors or inducers. However, it should be noted that CYP1A1 is induced in smokers. The subjects who are current smokers and those with recent history of smoking may have lower plasma concentrations of BAY 1163877.

Initial *in vitro* study results with BAY 1163877 indicate minor mechanism-based (irreversible) inhibition potential towards CYP 3A4. Since several commonly used drugs are metabolized by CYP 3A4, subjects should be proactively closely monitored for side effects of these comedications due to potentially increased systemic exposure.

In general, subjects should be closely monitored for side effects of all concomitant medications regardless of elimination pathway, especially those with narrow therapeutic index. If possible, narrow therapeutic index drugs that are CYP3A4 substrates should be avoided (see Section 16.11).

No data are available to evaluate the interaction between BAY 1163877 and radiation.

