In order to evaluate the relative bioavailability of the tablet formulation, tablet  $C_{max}/D$ ,  $AUC(0-t_{last})/D$  and AUC/D on Cycle 1, Day -3 will be compared to solution  $C_{max}/D$ ,  $AUC(0-t_{last})/D$ , AUC/D on Cycle 1, Day 1 for all analytes. If needed, additional PK parameters may be used for relative bioavailability assessment. The logarithms of these PK parameters will be analyzed using analysis of variance (ANOVA) including subject and formulation effects. Based on these analyses, point estimates (LS-means) and exploratory 90% confidence intervals for the ratios (tablet/solution) of  $C_{max}/D$ ,  $AUC(0-t_{last})/D$ , AUC/D will be calculated by retransformation of the logarithmic data using the intra-individual standard deviation of the ANOVA.

In order to evaluate the food effect, BAY 1163877  $C_{max}$  and AUC(0- $t_{last}$ ) on Cycle 1, Day -3 and  $C_{max}$  and AUC(0- $t_{last}$ ) on Cycle 1, Day 1 will be compared. The logarithms of  $C_{max}$  and AUC(0- $t_{last}$ ) will be analyzed using ANOVA including subject and food effects. Based on these analyses, point estimates (LS-means) and exploratory 90% confidence intervals for the ratios (high-fat, high-calorie meal / fasting) of  $C_{max}$  and AUC(0- $t_{last}$ ) will be calculated by retransformation of the logarithmic data using the intra-individual

17 Oct 2018 Version 8.0 Page: 107 of 395

standard deviation of the ANOVA.

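### The food and tablet comparisons each use one fixed order, so the reported ratio mixes the food or formulation effect with any difference between Day -3 and Day 1

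*Protocol*

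**What the plan says.** **Order.** Protocol section 8.4.2.1 gives the food-effect subjects single doses "on Cycle 1, Day -3 (after consumption of a high-fat, high-calorie breakfast) and on Cycle 1, Day 1", the second one fasted; sections 6 and 8.4.2.2.1 repeat this. For the tablet bridging cohort, section 6 describes a single dose "using the tablet formulation on Cycle 1, Day -3 followed by solution formulation starting Cycle 1 Day 1". No second order appears for either comparison, and section 8.3 states: "A random list is not necessary because this is a non-randomized open label clinical trial".

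**Analysis.** Section 10.4.5 compares Day -3 with Day 1. For food, log Cmax and log AUC(0-tlast) "will be analyzed using ANOVA including subject and food effects". For the tablet, the log dose-adjusted parameters "will be analyzed using analysis of variance (ANOVA) including subject and formulation effects". Each result is a point estimate with an exploratory 90% confidence interval, named as a fed/fasting or a tablet/solution ratio.

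**Size and use.** Section 6 plans approximately 8 food-effect subjects and at least 3 subjects with data for the tablet comparison; escalation cohorts may start with 3 or, optionally, 4. Relative bioavailability is a secondary objective in section 4. Section 6 adds that, depending on that result, subjects who started on solution may move to tablets. Section 10.1 says all intervals are to be read as exploratory.

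**The concern.** A within-subject comparison isolates food or formulation only if nothing else changes between the two doses. Here the day changes too, in the same direction for everyone. The sections cited state no assumption of equal exposure across days, plan no carry-over check and put no caveat on the ratio.

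The consequence is bias, not imprecision. The 90% interval does not reflect it, and more subjects dosed in the same order would not reduce it. A later analysis plan cannot repair it by modelling either, because the protocol has fixed the order. What is at stake is how two exploratory PK results are read: one can inform a change of formulation, and the other describes the effect of a high-fat meal. The MTD and the safety conclusions are not affected.

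**Working it through.** The protocol gives no effect size, variability or sample-size basis for either comparison, so there is no planned figure to reproduce.

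**1. What the planned estimate measures.** Let φ be the log food ratio (fed/fasting) and δ the log ratio of Day -3 to Day 1 exposure under the same condition. Each subject's log difference, fed on Day -3 minus fasted on Day 1, has mean φ + δ. The subject-plus-food ANOVA returns the average of these differences, so

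reported ratio = true food ratio × day ratio.

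The tablet comparison has the same form.

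**2. A period term does not help under this order.** With subject, treatment and period columns, the design matrix has rank 9 for 10 columns at n = 8, and rank 4 for 5 columns at n = 3. Treatment and period cannot be separated.

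**3. Size of the bias** (day effects are assumptions; true ratio 1.00):
- Day 1 exposure 5% higher: 1/1.05 = 0.95
- 10% higher: 1/1.10 = 0.91
- 15% higher: 1/1.15 = 0.87
- 20% higher: 1/1.20 = 0.83

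**4. How often the 90% interval would exclude 1 when food has no effect.** This describes the behaviour of the interval; the plan has no decision rule. Intra-subject CV is assumed at 20–40%. With s = √ln(1 + CV²), SE = s·√(2/n) and n = 8, the noncentral t on 7 df with noncentrality |ln(day ratio)|/SE gives:

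| Day effect | CV 20% | CV 30% | CV 40% |
|---|---|---|---|
| none | 10% | 10% | 10% |
| 5% | 13% | 12% | 11% |
| 10% | 22% | 16% | 13% |
| 15% | 36% | 22% | 17% |
| 20% | 51% | 30% | 22% |

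Example at CV 30% and 15%: s = 0.294, SE = 0.294 × √(2/8) = 0.147, noncentrality = 0.140/0.147 = 0.95, giving 22%.

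**5. Residual drug.** Section 9.4.1.1 places the 24 h and 48 h assessments on Days -2 and -1, so the Day 1 dose comes 72 h after the first. The fraction remaining is 0.5^(72/half-life): 0.02% at an assumed half-life of 6 h, 1.6% at 12 h and 12.5% at 24 h.

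**6. Two orders.** With fed first, the mean fed-minus-fasted difference is φ + δ; with fasted first it is φ − δ. The average of the two is φ. At n = 8, four per order, the matrix has full rank (10 of 10). In 10,000 simulated trials per setting (CV 30%, true ratio 1, day ratios 1.0 to 1.3), the estimate stayed at 1.00 and the interval excluded 1 in 10.1–10.6% of runs. Error df fall from 7 to 6, so at CV 30% the interval factor goes from exp(1.895 × 0.147) = 1.321 to exp(1.943 × 0.147) = 1.330.

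**7. Why not for the tablet cohort.** With 4 subjects, error df fall from 3 to 2. SE = 0.294 × √(2/4) = 0.208 at CV 30%, so the factor goes from exp(2.353 × 0.208) = 1.63 to exp(2.920 × 0.208) = 1.83. With 3 subjects only 1 df remains.

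**The case against.** Four stronger readings are tempting and are not supported.

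- **That section 10.4.5 wrongly omits a period term.** With one sequence the term is not estimable. Subject plus treatment is the fixed-effects model this design allows.
- **That the plan runs a test with an inflated error rate.** It plans point estimates and exploratory intervals, with no margin and no decision rule. The exclusion rates above only illustrate the shift.
- **That a day effect exists.** Section 8.9.1 says in vitro results "indicate minor mechanism-based (irreversible) inhibition potential towards CYP 3A4" and applies this to exposure of co-medications. It does not say that one dose slows the drug's own clearance 72 h later. A reader might infer lower clearance on Day 1; the documents do not establish it.
- **That neither ratio can be interpreted, or that the tablet result decides the switch.** The ratios are valid if there is no day effect, and section 6 says only that subjects may be switched.

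In mitigation, two drug-free days separate the doses, a Day 1 pre-dose sample is scheduled (section 9.4.2.1), and simple carry-over is negligible unless the half-life is long. At CV 20–40% the n = 8 interval already spans a factor of 1.206 to 1.440 either way, so a modest bias lies within its half-width.

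These arguments limit the severity but do not remove the point. The exploratory label concerns error control; a confounded estimate remains confounded. The pre-dose sample reveals residual drug only, not other differences between the days. The objection that reversing the order disturbs Day 1 data also stands in part: the 24-hour urine collection and the Day 1 primary parameters assume a common Day 1 condition, and the fix has to allow for that.

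**Conclusion.** The point holds as a matter of allocation order. Both comparisons alias treatment with day, and any day or carry-over difference passes one-for-one into a ratio labelled as food or formulation. That follows from the protocol text alone. How much it matters depends on assumptions the documents do not supply: a 15% higher Day 1 exposure would turn 1.00 into 0.87, a 5% difference would matter little, and with no day effect the planned analysis is valid. It should be changed for any food-effect subjects still to be dosed, because the remedy is cheap. Otherwise it calls for a stated assumption and an accurate label.

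**What to change.** **Food effect, subjects not yet dosed.** Randomise the approximately 8 subjects 1:1 to fed-then-fasted or fasted-then-fed on the same Day -3 and Day 1, and analyse log Cmax and log AUC(0-tlast) with subject, period and food. This needs a short allocation list and no added dose, visit, sample or subject. The costs are:
- one error df (factor 1.321 to 1.330 at CV 30%);
- fasted single-dose summaries must be selected by condition, not by day;
- urine should come from subjects fasted on Day 1 or from outside the food assessment.

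Two orders remove a common day effect. If carry-over differed between fed and fasted first doses, half of that difference would remain, so the Day 1 pre-dose level should still be examined.

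**Tablet bridging cohort, and food subjects already dosed in the fixed order.** Keep the existing model. Use the scheduled Day 1 pre-dose concentration to correct Day 1 exposure for residual drug. State in section 10.4.5 that the ratio assumes no period effect, and report it as tablet Day -3 versus solution Day 1, or fed Day -3 versus fasted Day 1. This costs a few sentences and one derived variable. The correction deals with residual drug only, so the assumption and the label are needed whatever the pre-dose values show.

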#### 10.4.6 Pharmacodynamic data

Cardiovascular parameters will be described by the following summary statistics: arithmetic mean, standard deviation, median, minimum and maximum. These summary statistics will be presented by cohort for the original data as well as for the difference to baseline.

Graphical displays of individual data as well as mean values with standard deviation will be included for absolute values as well as change from baseline.

#### 10.4.7 Efficacy data

Efficacy data, such as best tumor response, will be summarized using descriptive statistics and will be graphically displayed if appropriate. The correlation between pharmacodynamic parameters and selected safety, efficacy, or PK parameters may be graphically displayed. Further statistical analyses may be conducted.

The efficacy analysis will include descriptive analyses on response rate, progression-free survival (PFS) and time to progression (TTP).

**Response** as defined by RECIST v.1.1: complete response (CR), partial response (PR), stable disease (SD), progressive disease (PD), see Section 16.8.

**Progression-free survival (PFS)** is defined as the time (days) from the date of the first dose of study drug to the date of the first observed radiological disease progression or death, whatever comes first. PFS for subjects without tumor progression at the time of analysis will be censored at their last date of tumor evaluation.

**Time to progression (TTP)** is defined as the time from start of study treatment until objective tumor progression; TTP does not include deaths.

#### 10.5 Planned interim analysis

Safety data will be reviewed on an ongoing basis during study Part 1 / dose escalation (all comer). Bayesian dose-response and / or PK / PD modeling of DLTs rates and CTCAE v4.03 gradings may be performed after selected cohorts in order to generate additional relevant information for the adaptive dose selection decisions. The sponsor together with all investigators will review all available data and make the final decision as to dose-escalation, de-escalation or cohort expansion during the adaptive dose escalation part. This group will also determine when to implement predefined stopping rules.

No interim analysis is planned during dose expansion at MTD in study Part 1 (MTD expansion cohort "all comer"), study Part 2 (MTD expansion cohort "sqNSCLC + LAC + BC + SCCHN") or study part 3 (MTD expansion cohort "Safety cohort").84

.

 Part 3 - Safety cohort - was added by Amendment 7, see section 15.6.2.29

No. BAY 1163877 / 16443

17 Oct 2018 Version 8.0 Page: 108 of 395

### 10.6 Further analysis described and reported under separate cover

In order to evaluate the exposure-response during 4 cycles, two blood samples will be collected on Day 1 of Cycles 2-5, one before and one after a supervised dose. The resulting longitudinal exposure data will be modeled together with occurrences of selected adverse events and documented clinical responses. Also longitudinally measured PD biomarkers will be modeled with this exposure data. Exposure-response models and simulations after alternative dosing schedules will be reported in a separate document.

### 10.7 Determination of sample size - amended

This is primarily a descriptive safety and tolerability Phase I trial. No formal sample size estimation is performed. The actual sample size required to adequately determine the MTD depends on the initial dose, rate of dose escalation and the observed dose-toxicity and dose / exposure-pharmacological relationships. Simulation studies have been performed to quantify the operational characteristics (i.e., precision of the MTD, sample size, number of subjects being over / under dosed) of the adaptive dose-escalation design under a number of plausible dose-DLT relationship scenarios. Results are provided in Section 16.4. Based on experience the chosen sample size of 3-9 subjects per cohort is considered to be sufficient to fulfill the objectives of the study.

In study Part 1 / MTD expansion (all comer), additional subjects will be included in order to gain more information about biomarkers (p-ERK1/2) in at least 20 evaluable subjects with any solid tumors.

In study Part 2 / MTD expansion, additional subjects will be included in order to obtain further safety and PK data at the MTD level in at least 20 subjects with sqNSCLC or LAC, at least 30, up to a maximum of 50 evaluable subjects with BC and at least 8 subjects with SCCHN.85

In study Part 3 / MTD expansion "Safety cohort", additional subjects will be included to expand the safety database, to collect additional efficacy data, and to assess changes of immune parameters during treatment at the MTD level in approximately 20 subjects with sqNSCLC or LAC, and approximately 20 subjects with BC. 

### 11 Data handling and quality assurance

### 11.1 Data recording - amended

It is the expectation of the sponsor that all data entered into the eCRF has source documentation available at the study site. Entries into the eCRF should be made as soon as possible.

A Source Document Checklist will be used at site to identify the source data for all points

-

 Modified by Amendment 7, see section 15.6.2.30

 Part 3 - Safety cohort - was added by Amendment 7, see section 15.6.2.30

No. BAY 1163877 / 16443

17 Oct 2018 Version 8.0 Page: 109 of 395

### collected.

A CRO (Linical, formerly part of Nuvisan) provides the investigational site with access to an internet / web-based electronic data capture (EDC) computer system (termed "Inform"). Oracle has developed this system as a secured data entry tool that cannot be modified by investigative sites. The customized application for this protocol was developed by Linical and validated according to Linical "Standard Operating Procedures". Edit checks and data logic checks are done at the point of entry and are validated by Linical. All data entered into the system is transferred to a secure server maintained by Linical.

Access to the Inform EDC system at the site, at Linical and at Bayer is password protected. Study access is granted to site personnel only after they have been trained in the use of the Inform EDC System by Linical personnel or after a web-based training, either at the investigational site or at the investigators' meeting. Linical and Bayer personnel are also required to complete the training program before they are allowed to access the system. All Inform EDC system training history is documented and maintained by Linical.

The Inform EDC System contains a system-generated audit trail that captures any changes made to a data field, including who made the change, and the date and time it was made. This information is available both at the investigator's site and at Linical.

Data entries made in the Inform EDC screens are supported by source documents maintained for all subjects enrolled in this study.

• Results from pharmacokinetic analyses

The results of drug concentration measurements will be provided as electronic data files and transferred to Data Management, where the information necessary for evaluation will be added (e.g. administration and sampling time points, demographic data). This data set will be evaluated by the responsible pharmacokineticist. The complete pharmacokinetic evaluation will then be retransferred to Data Management.

